### **5.3.1 Laboratory Test Assessments**

A central and/or local laboratory will perform the analyses and will provide reference ranges for these tests.

Results of clinical laboratory tests performed on Day 1 must be available prior to dosing.

The following clinical laboratory tests will be performed:

#### **Hematology**

Hemoglobin	Hematocrit
Total leukocyte count, including differential	Platelet count

#### **Serum Chemistry**

AST	Total Protein
ALT	Albumin
TB	Sodium
Direct bilirubin (only if TB is elevated)	Potassium
Alkaline phosphatase	Chloride
Lactate dehydrogenase	Calcium
Creatinine	Phosphorus
Blood urea nitrogen or Urea	Magnesium
Uric acid	
Glucose	Creatine kinase with reflex measurement of isoenzymes if elevated

Troponin I or T at screening and Part 1 and Part 3A cycle 1 only.

#### **Part 3 only:**

Thyroid panel (including thyroid-stimulating hormone, free T3, and free T4)  
Amylase and Lipase (at screening only and as clinically indicated)

#### **Serology**

Serum for hepatitis C antibody (if hepatitis C antibody is positive reflex to hepatitis C RNA) or

hepatitis C RNA, Hepatitis B surface antigen, HIV-1, HIV-2 antibody (testing for HIV-1 and HIV-2 must be performed at sites where mandated by local requirements).

Screening only:  
FSH ([Section 3.3.3](#))

### Urinalysis

Protein	Leukocyte esterase
Glucose	Specific gravity
Blood	pH

Microscopic examination of the sediment if blood, protein or leukocytes esterase are positive on the dipstick

### Other Analyses

At the time of tumor assessments:

- CA125 for subjects with ovarian carcinoma and mesothelioma
- CA19-9 for subjects with pancreatic carcinoma

Pregnancy test (WOCBP only: screening, pre-dose [each dose of BMS-986148], EOT, and follow-up).

Results of all laboratory tests required by this protocol must be provided to BMS, either recorded on the laboratory pages of the CRF or by another mechanism as agreed upon between the investigator and BMS (eg, provided electronically). If the units of a test result differ from those printed on the CRF, the recorded laboratory values must specify the correct units. Any abnormal laboratory test result considered clinically significant by the investigator must be recorded on the appropriate AE page of the CRF (see [Section 6.3](#)).

## 5.4 Efficacy Assessments

Data for the tumor assessments specified in this protocol (see [Table 5.1-2](#) through [Table 5.1-8](#)) should be submitted to BMS. Additional assessments may be performed as part of standard of care; however, data for these assessments should remain in the subject's medical record and should not be provided to BMS unless specifically requested by the Sponsor. Sponsor can request scans for review at any time during or after the study.

### 5.4.1 Primary Efficacy Assessment

Tumor measurements with CT and/ or MRI, as appropriate, will be conducted at screening, at the start of Cycle 3, and then every 2 cycles ( $\pm 1$  week) during the treatment phase. Tumor measurements should be conducted earlier, if clinically indicated. Subjects with SD, PR, or CR at the last clinical follow-up visit undergo tumor assessment via CT/MRI scans every 3 to 4 months during the Survival Follow-up ([Sections 8.3.2.2](#) and [8.5](#)) phase until progression or death. Tumor measurements will be collected in all subjects until progression or the subject's

discontinuation from the study as per Table 5.1-2 to Table 5.1-8. Tumor response and progression will be evaluated in this study using RECIST version 1.1 criteria or Modified RECIST for malignant pleural mesothelioma (Appendix 4). Initial response assessment of PR or CR must be confirmed by a consecutive assessment no less than 4 weeks (28 days) later.

At the Sponsor's discretion, de-identified scans and measurements may be collected and reviewed by independent radiologists using RECIST version 1.1 criteria or Modified RECIST for malignant pleural mesothelioma at a later date or at any time during the study.

### **5.4.3 Imaging Assessment for the Study**

Any incidental findings of potential clinical relevance that are not directly associated with the objectives of the protocol should be evaluated and handled by the study investigator as per standard medical/clinical judgment.

#### **Computed Tomography/Magnetic Resonance Imaging**

Contrast-enhanced CT scans acquired on dedicated CT equipment is preferred for this study. CT with contrast of the chest, abdomen, and pelvis are to be performed for tumor assessments as indicated in Table 5.1-2 through Table 5.1-8. CT scans should be acquired with 5 mm slices with no intervening gap (contiguous).

Should a subject have a contraindication for CT IV contrast, a noncontrast CT of the chest and a contrast enhanced MRI of the abdomen and pelvis may be obtained. MRIs should be acquired with slice thickness of  $\leq 5$  mm with no gap (contiguous).

Every attempt should be made to image each subject using an identical acquisition protocol on the same scanner for all imaging time points.

It is the local imaging facility's responsibility to determine, based on subject attributes (eg, allergy history, diabetic history, and renal status), the appropriate imaging modality and contrast regimen for each subject. Imaging contraindications and contrast risks should be considered in this assessment. Subjects with renal insufficiency should be assessed as to whether or not they should receive contrast and if so, what type and dose of contrast is appropriate. Specific to MRI, subjects with severe renal insufficiency (ie, estimated glomerular filtration rate  $< 30$  mL/min/1.73m^2) are at increased risk of nephrogenic systemic fibrosis. MRI contrast should not be given to this subject population. In addition, subjects are excluded from MRI if they have tattoos, metallic implants, pacemakers, etc.

The ultimate decision to perform MRI in an individual subject in this study rests with the site radiologist, the investigator, and the standard set by the local Ethics Committee.

## 5.5 Pharmacokinetic and Immunogenicity Assessments

Serum samples for total antibody, active ADC, [REDACTED] and nivolumab PK assessments as well as plasma samples for [REDACTED] unconjugated tubulysin PK assessments will be collected in all subjects. Serum samples for antibody-drug antibody (ADA) assessments will also be collected in all subjects. The PK parameters to be assessed include:

Cmax	Maximum observed serum or plasma concentration
Tmax	Time of maximum observed serum or plasma concentration
AUC(0-t)	Area under the concentration-time curve from time 0 to the time of the last quantifiable concentration
AUC(TAU)	Area under the concentration-time curve in 1 dosing interval
Ctau	Concentration in a dosing interval
Ctrough	Trough observed serum or plasma concentration (this includes pre-dose concentrations and Ctau concentrations)
CLT	Total body clearance calculated as Dose divided by AUC(TAU)
Vss	Volume of distribution at steady state
Vz	Apparent volume of distribution at steady state
AI_AUC	AUC accumulation index; ratio of AUC(TAU) at steady-state to AUC(TAU) after the first dose
AI_Cmax	Cmax accumulation index; ratio of Cmax at steady-state to Cmax after the first dose
AI_Ctau	Ctau accumulation index; ratio of Ctau at steady-state to Ctau after the first dose
Cavg	Average concentration over a dosing interval calculated by dividing AUC(TAU) by tau
T-HALF	Terminal serum or plasma half-life

Individual subject PK parameter values will be derived by noncompartmental methods using a validated PK analysis program. Actual times will be used for the analyses.

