#### Endpoints:

**Primary Endpoints:** Incidence of AEs at worst grade, serious AEs (SAEs) at worst grade, AEs leading to discontinuations, deaths, and frequency of laboratory test toxicity grade shifting from baseline. Safety will be evaluated from the time that the subject signs the informed consent, and for up to 60 days (or 100 days for combination therapy) after the last dose of study drug.

**Pharmacokinetic:** Select PK parameters including Cmax, Tmax, AUC(0-t), AUC(TAU), Ctau, Ctrough, CLT, Vss, Vz, AI\_AUC, AI\_Cmax, AI\_Ctau, Cavg, and T-HALF will be assessed from serum and plasma concentration-time data collected during Cycle 1 and Cycle 4.

**Efficacy:** BOR, ORR, duration of response, PFS rate at select times [REDACTED].

**Immunogenicity:** Frequency of subject immunogenicity status.

**Electrocardiography (ECG):** Changes in QTcF ( $\Delta$ QTcF) from baseline at selected times.

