#### 5) Age and Reproductive Status

- a) Males and females, 18 years of age or greater or local age of majority.
- b) Women of childbearing potential (WOCBP) must have a negative serum or urine pregnancy test (minimum sensitivity 25 IU/L or equivalent units of human chorionic gonadotrophin) within 24 hours prior to the start of study drug.
- c) Women must not be breastfeeding. WOCBP must agree to follow instructions for method(s) of contraception for the duration of treatment with BMS-986148 monotherapy plus 5 half-lives of the total antibody (approximately 60 days) plus 30 days (duration of ovulatory cycle) for a total of 90 days post-treatment completion (Part 1 and Part 2).

WOCBP must agree to follow instructions for method(s) of contraception for the duration of treatment with BMS-986148 and nivolumab combination therapy for 23 weeks (30 days plus the time required for nivolumab to undergo 5 half-lives) after the last dose of study drug (Part 3).

- d) Males who are sexually active with WOCBP must agree to follow instructions for method(s) of contraception for the duration of treatment with BMS-986148 monotherapy plus 5 half-lives of the total antibody (approximately 60 days) plus 90 days (duration of sperm turnover) for a total of 150 days post-treatment completion (Part 1 and Part 2). If treated with BMS-986148 and nivolumab combination, males who are sexually active with WOCBP must continue contraception for 31 weeks (90 days plus the time required for nivolumab to undergo 5 half-lives) after the last dose of study drug (Part 3).
- e) Azoospermic males and WOCBP who are continuously not heterosexually active are exempt from contraceptive requirements. However, the latter must still undergo pregnancy testing as described in this section.

Investigators shall counsel WOCBP and male subjects who are sexually active with WOCBP on the importance of pregnancy prevention and the implications of an unexpected pregnancy. Investigators shall advise WOCBP and male subjects who are sexually active with WOCBP on the use of highly effective methods of contraception. Highly effective methods of contraception have a failure rate of < 1% when used consistently and correctly.

At a minimum, subjects must agree to use 1 highly effective method listed below:

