### **4.2 Secondary Endpoints**

#### **4.2.1 Pharmacokinetics**

The pharmacokinetics of total antibody, [REDACTED] active ADC, [REDACTED] and unconjugated tubulysin will be characterized using the following endpoints:

- Cmax: Maximum observed serum or plasma concentration
- Tmax: Time of maximum observed serum or plasma concentration
- AUC(0-t): Area under the concentration-time curve from time zero to time t
- AUC(TAU): Area under the concentration-time curve in one dosing interval
- Ctau: Concentration at the end of a dosing interval
- Ctrough: Trough observed serum or plasma concentration (includes pre-dose and Ctau concentrations)
- CLT: Total body clearance
- Vss: Apparent volume of distribution at steady state
- Vz: Volume of distribution of terminal phase

[figure not shown]

- AI\_AUC: AUC Accumulation Index; ratio of AUC(TAU) at steady state to AUC(TAU) after the first dose
- AI\_Cmax: Cmax Accumulation Index; ratio of Cmax at steady state to Cmax after the first dose
- AI\_Ctau: Ctau Accumulation Index; ratio of Ctau at steady state to Ctau after the first dose
- Cavg: average concentration over the dosing interval; AUC(TAU)/tau
- T-HALF: Terminal serum or plasma half life

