**Summary:**

Summary statistics will be provided for the following all listed parameters in [Section 4.2.1](#) by dose, dose regimen, study day and time.

Geometric means and coefficients of variation will be presented for all parameters after the first dose except Tmax and T\_HALF. Median, minimum, and maximum will be presented for Tmax, T\_HALF.

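### CLT is defined as Dose/AUC(TAU) with no steady-state condition, so a value derived after the first dose would overstate clearance, about 1.4-fold for total antibody on Q3W

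*Protocol*

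**What the plan says.** Protocol Section 5.5 defines CLT as "Total body clearance calculated as Dose divided by AUC(TAU") and AUC(TAU) as "Area under the concentration-time curve in 1 dosing interval". Neither line mentions steady state. Neither the protocol nor the SAP lists an AUC to infinity.

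The synopsis (Endpoints, Pharmacokinetic) names CLT in a list of parameters that "will be assessed from serum and plasma concentration-time data collected during Cycle 1 and Cycle 4". Protocol Section 8.3.2.1 applies the Section 5.5 parameters to total antibody, active ADC, unconjugated tubulysin and nivolumab, without tying CLT to a cycle.

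SAP Section 4.2.1 lists CLT by name only ("CLT: Total body clearance"), with no formula. SAP Section 7.7 summarises all Section 4.2.1 parameters by dose, regimen, study day and time, and states: "Geometric means and coefficients of variation will be presented for all parameters after the first dose except Tmax and T\_HALF". CLT is not among the exceptions.

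Protocol Section 5.5 also defines AI_AUC as the "ratio of AUC(TAU) at steady-state to AUC(TAU) after the first dose", so the plan itself allows for accumulation between the first dose and steady state.

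**The concern.** Dose/AUC(TAU) equals clearance only when AUC over one interval equals the single-dose AUC to infinity, and under linear kinetics that holds only at steady state. After a first dose, the exposure beyond the interval is left out of the denominator and the ratio is too large.

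If the text is followed as written, first-dose clearance would be too high for any analyte whose half-life is not short relative to tau. Clearance would then appear to fall from Cycle 1 to Cycle 4, and first-dose values would differ between QW and Q3W because tau differs. For an antibody-drug conjugate, a fall of that kind could be misread as time-dependent clearance. PK characterisation is a secondary objective, so these numbers would appear in the study report.

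**Working it through.** The documents state no clearance value or AUC fraction, so there is no figure of the plan's own to reproduce.

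**Inputs**
- Total-antibody half-life: Protocol 3.3.1, item 5, equates "5 half-lives of the total antibody (approximately 60 days"), giving 60/5 = 12 days.
- Nivolumab half-life: the same item gives 23 weeks as 30 days plus 5 half-lives, so (161 − 30)/5 = 26.2 days. It gives 31 weeks as 90 days plus 5 half-lives, so (217 − 90)/5 = 25.4 days.
- Tau: 21 days on Q3W. For QW, 7 days is assumed, because the PK sections give no number.
- Active ADC and unconjugated tubulysin half-lives: not given. A range is shown.
- Kinetics: one-compartment and linear (assumption).

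**Formulas** (h = half-life)
- First dose: AUC(TAU)/AUC(INF) = 1 − 2^(−tau/h). The overstatement factor is the reciprocal.
- Fourth Q3W dose: 1/(1 − 2^(−4·tau/h)).
- QW 3-on/1-off: the contributions of all earlier doses are superposed.

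**Total antibody, h = 12 days**
- Q3W, first dose: 2^(−21/12) = 0.297; AUC fraction 0.703; factor 1/0.703 = 1.42.
- Q3W, Cycle 4: 2^(−84/12) = 0.0078; factor 1/0.9922 = 1.008.
- Apparent change from Cycle 1 to Cycle 4: 1.008/1.42 = 0.71, a fall of about 29%.
- QW, first dose: 2^(−7/12) = 0.667; AUC fraction 0.333; factor 3.0. Against Q3W this is 3.0/1.42 = 2.1-fold, from tau alone.
- QW, Cycle 4 with a 7-day tau: 1.39 for the Day 1 interval and 1.14 for the Day 15 interval. The week off prevents a weekly steady state, so moving to Cycle 4 does not by itself cure this regimen.

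**QW, total cycle dose over 28-day AUC, h = 12 days**
- At Day 28 the three doses have residual fractions 2^(−28/12) = 0.198, 2^(−21/12) = 0.297 and 2^(−14/12) = 0.445; mean 0.314.
- Cycle 1: 1/(1 − 0.314) = 1.46, still biased.
- Cycle 4: 0.314 × 2^(−84/12) = 0.0025; factor 1.002, a bias of about 0.2%.

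**Nivolumab, Q3W, h = 25.4 to 26.2 days**
- If the formula were used after the first dose: AUC fraction 0.436 to 0.426; factor 2.29 to 2.35.
- Cycle 4: 1.11 to 1.12.

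**Other half-lives, first-dose factor**

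| Half-life (days, assumed) | Q3W | QW |
|---|---|---|
| 3 | 1.01 | 1.25 |
| 4 | 1.03 | 1.42 |
| 6 | 1.10 | 1.80 |
| 14 | 1.55 | 3.41 |

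A numerical simulation with a 1-hour infusion (h = 12 days, Q3W) gave 1.42 in Cycle 1 and 1.008 in Cycle 4. As a consistency check, under linear kinetics AI_AUC is itself the first-dose factor. An AI_AUC well above 1 would therefore contradict a first-dose CLT in the same report.

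**The case against.** **Is a first-dose CLT planned?** The synopsis speaks of selected parameters and pools the two cycles. The same list contains accumulation indices, which need both cycles and cannot exist after one dose. The SAP sentence on first-dose summaries cannot be fully literal for the same reason. SAP Section 8.2.4 defers to an internal PK harmonization document that is not supplied and might restrict CLT, and SAP Section 7.7 limits summaries to adequate profiles. This stands as a caution: a first-dose CLT is the natural reading, not a certainty. It does not remove an explicit, unconditional formula that no supplied text restricts.

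**Nivolumab.** A reader might infer that the SAP plans a first-dose nivolumab clearance inflated 2.3-fold. The documents do not support that. The SAP describes only Parts 1 and 2 and does not list nivolumab as an analyte, and Protocol 8.3.2.1 names no cycle. The 2.3 is conditional.

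**Every analyte.** A reader might extend the total-antibody figure to active ADC and tubulysin. Their half-lives are not given, and on Q3W, the regimen intended for Part 2, the bias would be negligible at 3 to 4 days or less.

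**Decisions.** A reader might infer harm to dose selection. No stated rule uses CLT. The Part 1B starting dose comes from modelling active ADC concentrations, dose proportionality uses Cmax and AUC(TAU), and attainment of steady state is judged from trough concentrations. No comparison of CLT across cycles or regimens is planned either, so the false contrasts would arise in reading the tables, not in a planned test.

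**Remedy.** First-dose AUC(INF) for total antibody needs about 30% extrapolation on Q3W and 67% on QW. QW sampling in Cycle 1 ends at Day 22, with nothing further until Cycle 3 Day 1. Population PK is optional in both documents and cannot be relied on as a substitute. These points stand and shape the fix.

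**Conclusion.** The concern holds for the definition and for any CLT derived from it before steady state. For total antibody the first-dose overstatement is about 42% on Q3W and about three-fold on QW, against about 1% at Cycle 4 on Q3W. For nivolumab at Cycle 4 it is 11 to 12%.

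The sizes rest on half-lives back-calculated from contraception windows, on one-compartment linear kinetics, and on a 7-day tau for QW. Nonlinear clearance would change the size; the first-dose AUC over one interval would still fall short of AUC to infinity.

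The consequence is confined to descriptive PK results. Safety, efficacy and escalation decisions are untouched. The change should be made because the artefact is predictable and cheap to remove, but the conduct of the trial does not depend on it.

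**What to change.** In Protocol 5.5 and SAP 4.2.1 and 7.7:

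1. **Q3W:** derive and summarise CLT as Dose/AUC(TAU) at Cycle 4 only. The Cycle 5 Day 1 predose sample closes the interval. For nivolumab, note the residual bias of about 11%.
2. **QW 3-on/1-off:** derive CLT as total cycle dose divided by AUC over the 28-day Cycle 4, also closed by the Cycle 5 Day 1 predose sample. Do not use this ratio in Cycle 1.
3. **First dose:** do not report Dose/AUC(TAU) as clearance. Report a first-dose CLT only as Dose/AUC(INF), adding AUC(INF) to the parameter list, and only for profiles whose extrapolated fraction is below a limit fixed in advance.
4. **SAP 7.7:** add CLT to the exceptions in the first-dose summary rule, other than under item 3.

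The cost is a few lines of text and no new samples. The downside is that few or no first-dose clearance estimates will remain for the long half-life analytes, and subjects who stop before Cycle 4 will contribute none from the Cycle 4 rule.

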### 5.5.1 Pharmacokinetics and Immunogenicity: Collection and Processing

Table 5.5.1-1 and Table 5.5.1-2 list the sampling schedules to be followed for the assessment of PK and ADA for the every 3 week (Q3W) and the QW for 3 weeks followed by 1 week off dosing regimens, respectively. Table 5.5.1-3 lists the sampling schedules to be followed for the assessment of PK and ADA for the Q3W dosing regimen in combination with nivolumab. Table 5.5.1-4 lists the sampling schedules to be followed for the assessment of PK and ADA for the Q3W dosing regimen during retreatment with BMS-986148 in combination with nivolumab. All time points are relative to the start of study drug administration. Pre-dose samples should be taken within 30 minutes before the start of dose administration. If the end of the infusion is delayed to beyond the nominal infusion duration, the collection of this sample should also be delayed accordingly. On-treatment PK samples are intended to be drawn relative to actual dosing days, if a dose occurs on a different day within the cycle due to delays or minor schedule adjustments, PK samples should be adjusted accordingly. Samples for ADA are to be collected prior to the administration of study drug. Further details of sample collection, processing, and shipment will be provided in the laboratory procedures manual. Serum samples designated for

PK [REDACTED] assessments may also be used for immunogenicity analysis, if required (eg, insufficient volume for complete immunogenicity assessment or to follow up on a suspected immunogenicity-related AE).

Table 5.5.1-1: PK and ADA Sampling Schedule for BMS-986148 Monotherapy Q3W Dosing Regimen				
Study Day of Sample Collection	Event	Time (Relative To Start of Infusion) Hour: Min	PK Sample (Serum and Plasma)	ADA Sample (Serum)
Cycle 1				
1	Predose	00:00	X	X
1	EOI a	01:00	X	
1		04:00	X	
2		24:00	X	
4		72:00	X	
8		168:00	X	
15		336:00	X	X
Cycle 2				
1	Predose	00:00	X	
1	EOI	01:00	X	
Cycle 3				
1	Predose	00:00	X	X
1	EOI	01:00	X	
Cycle 4				
1	Predose	00:00	X	X
1	EOI	01:00	X	
1		04:00	X	
2		24:00	X	
4		72:00	X	
8		168:00	X	
15		336:00	X	
Every 2 Cycles Starting at Cycle 5 (PK Only)				
1	Predose	00:00	X	
Every 5 Cycles Starting at Cycle 9 (PK and ADA)				
1	Predose	00:00	X	X
EOT			X	X

**Table 5.5.1-1: PK and ADA Sampling Schedule for BMS-986148 Monotherapy Q3W Dosing Regimen**

Study Day of Sample Collection	Event	Time (Relative To Start of Infusion) Hour: Min	PK Sample (Serum and Plasma)	ADA Sample (Serum)
30-Day Follow-Up			X	
60-Day Follow-Up			X	X
Event Driven c			X	X

a EOI = Sample must be collected immediately following the end of the infusion. End of Infusion Serum will be collected for measuring total antibody, [REDACTED] and active ADC concentrations. Plasma will be collected for measuring [REDACTED] unconjugated tubulysin concentrations.

c In the event that labs are drawn and the subject is not dosed.

ADA: anti-drug antibody; ADC: antibody-drug conjugate; EOI: end of infusion; EOT: end of treatment; min: minimum; PK: pharmacokinetics; Q3W: every 3 weeks.

**Table 5.5.1-2: PK and ADA Sampling Schedule for BMS-986148 Monotherapy QW Dosing Regimen**

Study Day of Sample Collection	Event	Time (Relative To Start of Infusion) Hour: Min	PK Sample (Serum and Plasma)	ADA Sample (Serum)
Cycle 1				
1	Predose	00:00	X	X
1	EOI a	01:00	X	
1		04:00	X	
2		24:00	X	
4		72:00	X	
8	Predose	00:00	X	
8	EOI	01:00	X	
15	Predose	00:00	X	X
15	EOI	01:00	X	
22		168:00	X	
Cycle 3				
1	Predose	00:00	X	X
Cycle 4				

